# 12.2.6 King's ALS Clinical Stage Derived from ALSFRS-R Score and Death Event

The King's ALS clinical stage at each visit will be calculated by the Sponsor using ALSFRS-R and death event.

# 12.3 Exploratory Efficacy Assessments

# 12.3.1 Exploratory Biomarker Assessments

#### 12.3.2 Optional Biomarker Assessment

Optional biomarker samples (whole blood, plasma, or serum) approximately 20 mL, will be collected at the time points described in Table 1 where local regulations and IRB/ECs allow, on subjects who provide consent. At the Sponsor's discretion, potential future testing of exploratory biomarkers related to ALS-related disease and edaravone treatment response may include, but is not limited to, markers of

Whole blood samples will be collected and stored for potential future Ribonucleic acid (RNA) expression profiling of ALS disease activity and/or edaravone treatment response (RNA testing to be performed at the Sponsor's discretion). The purpose of RNA collection is to develop potential predictive biomarkers through identification of gene expression patterns at baseline that may predict the clinical response (ie, efficacy and/or safety) to edaravone treatment and to develop potential pharmacodynamic markers through characterization of changes in blood cell gene expression induced by edaravone.

# 12.3.3 Nerve Conduction Testing/Electrophysiologic Assessment

At study sites selected by the Sponsor, and for subjects who consent, the Investigator (or subinvestigator) will measure the parameters (%CMAP, MUNIX, SNAP, and SNCV) using the nerve conduction test as described in Table 1. The evaluation results, together with the dates of evaluation, will be recorded in the eCRF. The methods and details will be outlined in the Study Reference Manual.

#### 12.4 Pharmacokinetic Assessments

At study sites selected by the Sponsor, and for subjects who consent, blood samples will be collected for PK determination of oral edaravone. The visit window at Week 4 and Week 12 for subjects who participate in PK collection will be restricted to +3 days. Sampling time points are set at times indicated in Table 1. The date and time for each blood sample and meals before and after study drug administration will be recorded in the source documents and eCRF.

Refer to the Central Laboratory Manual for details on collection, preparation, and storage.

# 12.5 Pharmacogenomic Sampling

For subjects who consent, a single 8.5 mL blood sample will be collected for pharmacogenomic analysis where local regulations and IRB/ECs allow as specified in Table 1. These samples will be used to investigate variable responses to edaravone and to investigate genetic variants both known and unknown thought to play a role in ALS and/or associated conditions. Assessment of variable response may include evaluation of AEs or differences in efficacy. All pharmacogenomic samples will be coded with the subject number.

Samples will be destroyed according to a process consistent with local regulations. Samples

will be retained for a maximum of 15 years after the last subject visit for the study, or for a shorter period if local regulations and/or IECs impose shorter time limits, at a facility selected by the Sponsor. This retention period enables use of new technologies, response to regulatory questions, and investigation of variable response that may not be observed until later in drug development or when the drug is commercially available. Molecular technologies are expected to improve during the 15-year storage period and therefore cannot be specifically named. However, existing approaches include whole genome or exome sequencing, genome wide association studies, candidate gene studies, and epigenetic analyses. Regardless of technology utilized, genotyping data generated will be used only for the specific research.

#### 13 SAFETY ASSESSMENTS

#### 13.1 Physical Examination

A full physical examination will consist of an assessment of major body parts and systems: abdominal, cardiovascular, general appearance, head, eyes, ears/nose/throat, lymph nodes, musculoskeletal, neck, neurological, dermatological, respiratory, and 'other'.

A routine physical examination will consist of an assessment of the following body systems: abdominal, cardiovascular, general appearance, respiratory, neurological, and other.

Abnormalities of clinical significance will be reported as AEs.

#### 13.2 Vital Signs

The following measurements will be performed: sitting systolic and diastolic blood pressure, heart rate (eg, beats per minute), respiratory rate, and axillary, oral, temporal (skin-based), or tympanic body temperature (eg, Celsius) and the same method is to be used throughout the study. Subjects must be in a supine position in a rested and calm state for at least 5 minutes before blood pressure assessments are conducted. If the subject is unable to be in the supine position, the subject should be in the most recumbent position as possible. The position selected for a subject should be the same that is used throughout the study and documented on the CRF.

The Investigator will perform an overall evaluation for safety purposes and the recording will be reported as 'normal', 'abnormal CS', or 'abnormal not clinically significant (NCS)'.

Abnormalities of clinical significance will be reported as AEs. Repeat measurements will be performed if needed.

#### 13.3 Orthostatic Hypotension

In addition to standard systolic and diastolic blood pressure assessments, the subject will be assessed for the presence of orthostatic hypotension. Subjects must be in a seated position in a rested and calm state for at least 5 minutes before orthostatic blood pressure assessments are conducted. Measure blood pressure and heart rate. Have the subject stand. Repeat blood pressure and heart rate measurements after standing 1 and 3 minutes. A drop in systolic blood pressure of  $\geq 20$  mm Hg, or in diastolic blood pressure of  $\geq 10$  mm Hg or increase in heart rate  $\geq 20$  beats/minute or clinical orthostatic symptoms (eg, experiencing lightheadedness or dizziness) is considered abnormal. Results from the orthostatic evaluation will be recorded as "abnormal" or "normal" in the CRF. If subjects cannot stand due to disease progression or other reasons, it will not be considered a protocol deviation.

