#### 13.4 Unsteadiness and Sensory Evaluation

Assessment of unsteadiness and peripheral sensation will be evaluated by interview and assessment of vibratory sensation with a tuning fork applied to the lateral side of the right and left ankles. The Investigator (or subinvestigator) will check for the following at each visit:

- Numbness: present/absent (if present record severity)
- Unsteadiness (eg, unsteadiness/dizziness; standing/sitting): present/absent (if present record severity)
- Vibratory sensation (with a tuning fork applied to the lateral side of the right and left ankles): Seconds (measure time of vibration that is felt when the handle of a vibrating 128 Hz tuning fork is put against the outer ankle)

If present, the severity will be graded on the following 3-point scale:

- Mild: The event does not interfere with activities of daily living
- Moderate: The event interferes to some extent with activities of daily living
- Severe: The event interferes significantly with activities of daily living

Abnormalities of clinical significance will be reported as AEs. Repeat measurements will be performed as needed.

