#### **Orthostatic Hypotension**

The number and percentage of "abnormal" by the Investigator in orthostatic hypotension will be summarized at each visit by treatment group.

For evaluation ("Normal/Abnormal") by the Investigator in vital signs, a shift table of the change from baseline will be summarized at each visit by treatment group.

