8.4.3.6. Vital Signs

The following measurements will be performed: sitting systolic and diastolic blood pressure, heart rate (eg, beats per minute), respiratory rate, and axillary, oral, temporal (skin-based), or tympanic body temperature (eg, Celsius). The Investigator will perform an overall evaluation for safety purposes and the recording will be reported as 'normal', 'abnormal clinically significant (CS)', or 'abnormal not clinically significant (NCS)'.

Criteria of Potentially Clinically Significant Values (PCSV) for Vital⁷

The following criteria to determine risk for PCSV for Vital signs are defined:

HR* at post-baseline ≤ 50 bpm and decrease from baseline ≥ 15 bpm

HR* at post-baseline ≥ 120 bpm and increase from baseline ≥ 15 bpm

SBP at post-baseline ≤ 90 mmHg and decrease from baseline ≥ 20 mmHg

SBP at post-baseline ≥ 180 mmHg and increase from baseline ≥ 20 mmHg

DBP at post-baseline ≤ 50 mmHg and decrease from baseline ≥ 15 mmHg

DBP at post-baseline ≥ 105 mmHg and increase from baseline ≥ 15 mmHg

Note: *HR will be regarded as Pulse Rate.

Orthostatic Hypotension

Orthostatic hypotension will be defined as experiencing lightheadedness and/or dizziness and/or a reduction in systolic BP of 20 mmHg or more, and/or a reduction in diastolic BP of 10 mmHg or more, or increase in heart rate > 20 beats/minute for the standing measurement compared to the supine measurement.

The following criteria to determine "Orthostatic vital sign changes" are defined:

- Decrease of ≥ 20 mmHg from 'Seated (resting 5 minutes)' Systolic Blood pressure to 'Standing (after 1 minute)' Systolic Blood pressure
- Decrease of ≥ 20 mmHg from 'Seated (resting 5 minutes)' Systolic Blood pressure to 'Standing (after 3 minutes)' Systolic Blood pressure
- Decrease of ≥ 10 mmHg from 'Seated (resting 5 minutes)' Diastolic Blood pressure to 'Standing (after 1 minute)' Diastolic Blood pressure
- Decrease of ≥ 10 mmHg from 'Seated (resting 5 minutes)' Diastolic Blood pressure to 'Standing (after 3 minutes)' Diastolic Blood pressure
- Increase of > 20 bpm from 'Seated (resting 5 minutes)' Pulse rate to 'Standing (after 1 minute)' Pulse rate

- Increase of >20 bpm from 'Seated (resting 5 minutes)' Pulse rate to 'Standing (after 3 minutes)' Pulse rate

The Investigator will also evaluate any clinical symptoms due to the orthostatic vital sign changes such as dizziness and lightheadness.

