9.3.4. Vital Signs

Vital sign measurements and their change from baseline will be listed and summarized using descriptive statistics by visit up to week 48. Those parameters will include: heart rate (HR), supine and standing blood pressure (BP) (both systolic and diastolic), body temperature and weight. Furthermore, orthostatic vital sign and supine minus standing blood pressure (both systolic and diastolic) and their change from baseline will be summarized with descriptive statistics by visit.

Vital sign values will be considered PCSV if they meet both criteria of the observed value and the change from baseline listed in section 8.4.3.6. The number and percentage of subjects with PCSV at any time post-baseline will be tabulated. The percentages will be calculated from the number of subjects with a baseline value and any time post-baseline value. The number and percentage of subjects with orthostatic hypotension as defined in section 8.4.3.6 will be summarized in the same way.

9.3.5. 12-Lead ECGs

All ECGs parameters will be listed and analyzed.

The ECGs will be assessed by the investigator and deemed “Normal”, “Abnormal, not clinically significant” (Abnormal, NCS) and “Abnormal, clinically significant” (Abnormal, CS) and tabulated by visit up to week 48 using frequency counts and percentages.

In addition, the numerical ECG parameters and their change from baseline generated by the central ECG laboratory (see section 8.4.3.5) will be summarized by descriptive statistics for each parameter by visit.

ECG parameters values will be considered PCSV if they meet the criteria listed in section 8.4.3.5. The number and percentage of subjects with PCSV will be tabulated. The percentages are to be calculated from the number of subjects with available baseline values and any time post-baseline value for a specific category.

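### The SAP counts dizziness or a heart-rate rise alone as orthostatic hypotension, so the one stated incidence mixes subjects with and without a blood-pressure fall

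*Protocol*

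**What the plan says.** **Protocol 13.3** has the subject sit, then stand, with readings at 1 and 3 minutes. Four criteria are joined by *or*: a systolic fall of at least 20 mmHg, a diastolic fall of at least 10 mmHg, a heart-rate rise of at least 20 beats/minute, "or clinical orthostatic symptoms (eg, experiencing lightheadedness or dizziness) is considered abnormal". The outcome is a single normal/abnormal entry ("Results from the orthostatic evaluation will be recorded as" one or the other). Protocol 17.4.5.9 plans a table of the abnormal calls "by the Investigator in orthostatic hypotension will be summarized at each visit by treatment group".

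**SAP 8.4.3.6** attaches the diagnosis to the composite: "Orthostatic hypotension will be defined as experiencing lightheadedness and/or dizziness and/or a reduction in systolic BP of 20 mmHg or more", with a diastolic limb of 10 mmHg, "or increase in heart rate > 20 beats/minute for the standing measurement compared to the supine measurement". The same section then lists six purely numerical criteria for orthostatic vital sign changes: systolic, diastolic and pulse, each at 1 and at 3 minutes, from a seated reference.

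**SAP 9.3.4** sets the output: "The number and percentage of subjects with orthostatic hypotension as defined in section 8.4.3.6 will be summarized in the same way". The model it follows is the count of potentially clinically significant values at any time after baseline. The section also says that "orthostatic vital sign and supine minus standing blood pressure (both systolic and diastolic) and their change from baseline will be summarized" by visit with descriptive statistics.

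**The concern.** Two of the four routes into the SAP definition need no fall in blood pressure. A subject whose pressure holds steady, or rises, on standing is still counted if dizzy or if the pulse rises enough. The SAP also drops the Protocol's requirement that the symptom be orthostatic.

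Orthostatic hypotension is a named safety endpoint, and comparing the safety of daily and on/off dosing is the secondary objective. The composite is the only clearly stated subject-level incidence of that endpoint. A reader of the safety table will take the row to mean blood-pressure falls, and will compare the regimens on a figure that may largely reflect something else.

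A smaller related point is that dizziness is also an example in the separate item in Protocol 13.4, "Unsteadiness (eg, unsteadiness/dizziness; standing/sitting): present/absent (if present record severity". One complaint can therefore appear in two safety summaries.

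**Working it through.** The documents give no rate, effect size or power for orthostatic hypotension, so there is no planned figure to reproduce. The check is of the wording first, then an illustration with assumed rates.

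**Wording.** For a subject with no systolic or diastolic fall who reports dizziness on standing:

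- Protocol 13.3: abnormal orthostatic evaluation.
- SAP 8.4.3.6: orthostatic hypotension.
- SAP 9.3.4: counted in the orthostatic hypotension row.
- SAP 9.3.4 postural-difference summary: contributes an unremarkable value to a mean.

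The result is the same if the only finding is a heart-rate rise.

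**Illustration.** Let *p* be the proportion of an arm with a qualifying pressure fall. Let *q* be the probability of qualifying on heart rate or symptoms, independent of *p*. The composite rate is

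1 − (1 − p)(1 − q).

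If *q* is the same in both arms, the difference between arms becomes (p₁ − p₀)(1 − q). The share of positives in an arm with no pressure fall is 1 − p / composite.

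*Equal q in both arms, p = 10% against 20% (difference 10 points, ratio 2.0):*

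| q | Composite rates | Difference (points) | Ratio | No pressure fall, lower-rate arm |
|---|---|---|---|---|
| 5% | 14.5% vs 24.0% | 9.5 | 1.66 | 1 − 0.10/0.145 = 31% |
| 10% | 19.0% vs 28.0% | 9.0 | 1.47 | 1 − 0.10/0.19 = 47% |
| 20% | 28.0% vs 36.0% | 8.0 | 1.29 | 1 − 0.10/0.28 = 64% |
| 30% | 37.0% vs 44.0% | 7.0 | 1.19 | 1 − 0.10/0.37 = 73% |

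*Unequal q:*

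- p = 5% in both arms, q = 10% vs 20%: 1 − 0.95 × 0.90 = 14.5% against 1 − 0.95 × 0.80 = 24.0%. A 9.5-point difference (ratio 1.66) appears with no difference in pressure falls.
- p = 5% vs 10%, q = 10% vs 20%: 14.5% against 1 − 0.90 × 0.80 = 28.0%. The difference grows from 5.0 to 13.5 points.
- p = 10% vs 20%, q = 20% vs 10%: 1 − 0.90 × 0.80 = 28.0% against 1 − 0.80 × 0.90 = 28.0%. A 10-point difference in pressure falls vanishes.

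So the direction of the distortion depends on how *q* compares between arms, and the documents give nothing to settle that.

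**The case against.** The strongest reply is that a sensitive composite is a legitimate safety screen and that the pressure information is reported elsewhere. Much of this stands:

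- SAP 8.4.3.6 lists pressure-only criteria, SAP 9.3.4 summarizes the postural difference and its change from baseline, vital signs are listed, and low standard blood-pressure values have their own significance counts. A reader might infer that the composite hides the pressure signal. It does not. What is missing is a clear commitment to count subjects meeting the postural pressure criteria alone, and a mean postural change can conceal a few subjects with large falls.
- A reader might infer that a regimen difference is always diluted. That needs *q* to be about equal in the two arms. Otherwise the composite can enlarge, create or cancel a difference.
- A reader might infer a loss of power. No test is specified for this table, which gives counts and percentages only, so no planned test can lose power. The figures above show loss of contrast.
- A reader might infer that the extra positives are unsteadiness from ALS. Unsteadiness is not a criterion in either document, the Protocol limits symptoms to orthostatic ones, subjects who cannot stand need not be tested, and no rate is given. Dizziness appearing in two untested summaries is an overlap, not an error.
- The Protocol's own term for the result is abnormal, which is accurate. The difficulty comes mainly from the SAP's definition, although the Protocol 17.4.5.9 table also carries the hypotension heading.

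The last sentence of SAP 8.4.3.6 also ties symptoms to the measured orthostatic changes. That suggests a narrower intent, but it is an additional investigator evaluation and does not alter the definition, whose limbs stay joined by *and/or*. Nor does it affect the heart-rate limb.

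**Conclusion.** The point holds as a labelling and reporting defect in SAP 8.4.3.6 and 9.3.4. Followed as written, the plan reports some subjects with no blood-pressure fall as having orthostatic hypotension, and the only clearly stated incidence of that endpoint combines the two kinds of case. This part rests on the text alone.

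The size is unknown. Under the assumed 10% and 20% pressure-fall rates with equal extra positives of 5% to 30%, the ratio between arms falls from 2.0 to between 1.66 and 1.19, and 31% to 73% of the lower-rate arm's positives have no pressure fall. If the extra positives differ by regimen, the error can go either way. These results depend on the assumed rates and on independence of the two routes.

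The point is minor. It affects how one descriptive safety row is read, and touches neither the efficacy analyses nor any planned test.

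**What to change.** In SAP 8.4.3.6 and 9.3.4:

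1. Report orthostatic hypotension as the number and percentage of subjects meeting the pressure criteria already listed: a systolic fall of at least 20 mmHg or a diastolic fall of at least 10 mmHg, at 1 or 3 minutes.
2. Show the heart-rate rise as a separate row.
3. Show orthostatic symptoms as a separate row if the CRF records them separately. Check this first, because Protocol 13.3 describes only one normal/abnormal entry.
4. Keep the any-criterion composite and the investigator's normal/abnormal call, each labelled *abnormal orthostatic evaluation* and identified by source (derived or investigator).

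While the section is open, reconcile two neighbouring inconsistencies, which are separate from this point: the heart-rate cut-off (at least 20 in Protocol 13.3, above 20 in the SAP) and the reference position (seated in Protocol 13.3 and the SAP's criteria list, supine in the SAP's definition and in 9.3.4).

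The cost is SAP wording and a few table rows. The pressure and pulse rows use readings the Protocol already requires. The reported incidence of orthostatic hypotension can only stay the same or fall compared with the composite, and a footnote should say why.

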#### 13.4 Unsteadiness and Sensory Evaluation

Assessment of unsteadiness and peripheral sensation will be evaluated by interview and assessment of vibratory sensation with a tuning fork applied to the lateral side of the right and left ankles. The Investigator (or subinvestigator) will check for the following at each visit:

- Numbness: present/absent (if present record severity)
- Unsteadiness (eg, unsteadiness/dizziness; standing/sitting): present/absent (if present record severity)
- Vibratory sensation (with a tuning fork applied to the lateral side of the right and left ankles): Seconds (measure time of vibration that is felt when the handle of a vibrating 128 Hz tuning fork is put against the outer ankle)

If present, the severity will be graded on the following 3-point scale:

- Mild: The event does not interfere with activities of daily living
- Moderate: The event interferes to some extent with activities of daily living
- Severe: The event interferes significantly with activities of daily living

Abnormalities of clinical significance will be reported as AEs. Repeat measurements will be performed as needed.

#### 13.5 Body Weight and Height

Body weight will be measured and recorded in pounds or kilograms, at time points mentioned in Table 1.

Height will be collected in inches or centimeters at screening only, at time points mentioned in Table 1.

## 13.6 12-lead Electrocardiogram

A 12-lead ECG will be performed after the subject has rested for at least 5 minutes in a supine position. The ECG must include the following measurements: R wave to R wave (RR) interval, heart rate, QRS, QT, corrected QT interval by Bazett (QTcB), and corrected QT interval by Fridericia (QTcF). The Investigator will perform an overall evaluation of the ECG for safety purposes and the recording will be reported as 'normal', 'abnormal CS', or 'abnormal NCS'. Abnormalities of clinical significance will be reported as AEs. Repeat measurements will be performed if needed.

#### 13.7 Clinical Laboratory Tests

Blood will be drawn at assigned timepoints for laboratory assessment (refer to Table 1 for further details).

As a guideline, the volume of blood to be sampled per time point shall be approximately 10 mL and the volume of the urine aliquot to be sampled per time point shall be approximately 15 to 20 mL.

#### 13.7.1 Hematology

Red blood cell count, hemoglobin, hematocrit value, white blood cell (WBC) count including differential, and platelet count.

# 13.7.2 Blood Chemistry

Albumin, total protein, AST, ALT, lactate dehydrogenase, alkaline phosphatase (ALP), creactive protein, total bilirubin, direct bilirubin, creatine kinase, total cholesterol, triglycerides, blood urea nitrogen, bicarbonate, serum glucose, serum creatinine level, uric acid, sodium (Na), potassium (K), chloride, calcium (Ca), and cystatin C. Vitamin B6 will be measured at the time points described in Table 1.

#### 13.7.3 Urinalysis (qualitative)

Protein, glucose, occult blood, WBCs, urobilinogen, and bilirubin.

